2.2 Randomization

No randomization will be conducted for this study.

2.3 Blinding

This is an open-label study. No blinding is needed.

2.4 Schedule of Assessments

[Table 1](#) and [Table 2](#) below present a schedule of study assessments.

Table 1 Schedule of Assessments for Group A

Period	Baseline	Treatment Period														1-Week Safety Follow-up
		3	4	5	6	7	8	9	10	11	12	13	14	15	16/ET ^b	Telephone Call
Visit ^a	2	3	4	5	6	7	8	9	10	11	12	13	14	15	16/ET ^b	Telephone Call
Assessment Week/Month	0	W1	W2	M1	M2	M3	M4	M5	M6	M7	M8	M9	M10	M11	M12	W53
Assessment Day	0	7	14	30	60	90	120	150	180	210	240	270	300	330	360	367
Concomitant medications	✓	✓	✓	✓	✓	✓	✓	✓	✓	✓	✓	✓	✓	✓	✓	✓
Adverse Events	✓	✓	✓	✓	✓	✓	✓	✓	✓	✓	✓	✓	✓	✓	✓	✓
Access IWRS	✓	✓	✓	✓	✓	✓	✓	✓	✓	✓	✓	✓	✓	✓	✓	
Investigational product dispensed	✓	✓	✓	✓	✓	✓	✓	✓	✓	✓	✓	✓	✓	✓		
Investigational product returned		✓	✓	✓	✓	✓	✓	✓	✓	✓	✓	✓	✓	✓	✓	
Investigational product compliance		✓	✓	✓	✓	✓	✓	✓	✓	✓	✓	✓	✓	✓	✓	

ADHD-RS-5 =Attention-deficit/Hyperactivity Disorder-Rating Scale 5, Child, Home Version; BMI=body mass index; CGI-I=Clinician’s Global Impressions – Improvement; CGI-S=Clinician’s Global Impressions – Severity of Illness; CSHQ=Children’s Sleep Habits Questionnaire; C-SSRS=Columbia-Suicide Severity Rating Scale; ECG=electrocardiogram; ET=early termination; IWRS=interactive web response system; M=month; MINI-KID=Mini International Neuropsychiatric Interview for Children and Adolescents; PSQ=Post Sleep Questionnaire; W=week.

^a Visit windows are with respect to baseline (Visit 2): ±2 days for Visit 3-4 and ±5 days for Visit 5-16 during treatment period, and +2 days for the safety follow up telephone call.

^b Subjects who terminate early will undergo the evaluations listed for Visit 16.

^c Inclusion/exclusion criteria will be reviewed at baseline (Visit 2).

^d Medical history will include all lifetime psychiatric and nonpsychiatric medications and procedures.

^e Vital signs include oral or tympanic temperature, pulse, sitting blood pressure, and respiratory rate. The subject will have been seated for a minimum of 3 minutes before blood pressure, pulse, and respiratory rate measurements are taken. Measurement of blood pressure and pulse will be collected 3 times (with at least 2 minutes in between each collection) using the provided age-appropriate cuff. The average of each set of 3 measurements will be used to determine continued participation in the study.

^f Blood pressure and pulse rate will be measured at each study visit. Temperature and respiratory rate will be measured at baseline (Visit 2).

^g Height and weight will be measured without shoes and with light clothing using a stadiometer for height and calibrated scale for weight.

^h Clinical laboratory evaluations will include hematology, biochemistry, endocrinology, and urinalysis.

ⁱ Electrocardiograms will be recorded in triplicate with at least 3 minutes in between each collection at baseline only.

^j Whenever possible, the same individual should complete/rate consistently the following scales and questionnaires as appropriate: ADHD-RS-5, CGI-I, and subject check to remain in the study; PSQ, and CSHQ. Include assessment of decreased appetite.

^k C-SSRS Pediatric/Cognitively impaired “Since Last Visit” version is completed for all visits. The scale will be compared with the C-SSRS Pediatric/Cognitively impaired

Table 1 Schedule of Assessments for Group A

Period	Baseline	Treatment Period														1-Week Safety Follow-up
		3	4	5	6	7	8	9	10	11	12	13	14	15	16/ ET ^b	Telephone Call
Visit ^a	2	3	4	5	6	7	8	9	10	11	12	13	14	15	16/ ET ^b	Telephone Call
Assessment Week/Month	0	W1	W2	M1	M2	M3	M4	M5	M6	M7	M8	M9	M10	M11	M12	W53
Assessment Day	0	7	14	30	60	90	120	150	180	210	240	270	300	330	360	367

^a“Baseline” from the antecedent study.

^b For females of child-bearing potential only.

Table 2 Schedule of Assessments for Group B

Period	Screening/ Washout ^a		Baseline	Treatment Period														1-Week Safety Follow- up
	1	Phone call		2	3	4	5	6	7	8	9	10	11	12	13	14	15	16/ ET ^c
Assessment Week/Month	-5 to -1		0	W1	W2	M1	M2	M3	M4	M5	M6	M7	M8	M9	M10	M11	M12	W53
Assessment Day ^b	-32 to - 3		0	7	14	30	60	90	120	150	180	210	240	270	300	330	360	367

ADHD-RS-5 =Attention-deficit/Hyperactivity Disorder-Rating Scale 5, Child, Home Version; BMI=body mass index; CGI-I=Clinician’s Global Impressions – Improvement; CGI--S=Clinician’s Global Impressions – Severity of Illness; CSHQ=Children’s Sleep Habits Questionnaire; C-SSRS=Columbia-Suicide Severity Rating Scale; ECG=electrocardiogram; ET=early termination; IWRS=interactive web response system; M=month; MINI-KID=Mini International Neuropsychiatric Interview for Children and Adolescents; PSQ=Post Sleep Questionnaire; W=week.

- ^a Following successful screening, a site representative will contact the subject’s parent/LAR to instruct the subject on discontinuing any prohibited medication for the washout period.
- ^b Visit windows are with respect to baseline (Visit 2): ±2 days for Visit 3-4 and ±5 days for Visit 5-16 during treatment period, and +2 days for the safety follow-up telephone call.
- ^c Subjects who terminate early will undergo the evaluations listed for Visit 16.
- ^d Inclusion/exclusion criteria will be reviewed during the washout telephone call and at baseline (Visit 2).
- ^e Medical history will include all lifetime psychiatric and nonpsychiatric medications and procedures.
- ^f Whenever possible, the same individual should complete/rate consistently the following scales and questionnaires as appropriate: ADHD-RS-5, CGI-S/I, and subject check to remain in the study; PSQ and CSHQ. Include assessment of decreased appetite.
- ^g If >32 days have elapsed since the screening evaluation was completed at Visit 1, then the following evaluations must be repeated at baseline (Visit 2): vital signs, clinical laboratory evaluations, and ECGs in triplicate. The physical examination will be abbreviated with a review of the following body systems: general appearance, respiratory, and cardiovascular.
- ^h Height and weight will be measured without shoes and with light clothing using a stadiometer for height and calibrated scale for weight
- ⁱ For females of child-bearing potential only
- ^j Vital signs include oral or tympanic temperature, pulse, sitting blood pressure, and respiratory rate. The subject will have been seated for a minimum of 3 minutes before blood pressure, pulse, and respiratory rate measurements are taken. Measurement of blood pressure and pulse will be collected 3 times (with at least 2 minutes in between each collection) using the age-appropriate cuff.
- ^k Blood pressure and pulse rate will be measured at each study visit. Temperature and respiratory rate will be measured at screening (Visit 1) only.
- ^l Clinical laboratory evaluations will include hematology, biochemistry, endocrinology, and urinalysis.
- ^m ECGs will be recorded in triplicate with at least 3 minutes in between each collection at screening only and at baseline only if >32 days have elapsed since the screening evaluation was completed at Visit 1.

2.5 Determination of Sample Size

Approximately 80 subjects will be enrolled into this study to ensure 60 subjects complete at least 6 months of study treatment. Subjects will enroll into this study from antecedent studies, SHP465-112 or SHP465-309 as well as de novo subjects who will be enrolled directly. The sample size was established to provide long-term safety data in children aged 4 to 12 years and will include at least 40 subjects aged 4-5 years at the time of informed consent in the antecedent study or this study, if directly enrolled. The sample size for this study is not based on statistical considerations.

2.6 Multiplicity Adjustments for Type I Error Control

Efficacy and safety data will be summarized descriptively for this study. No formal statistical tests will be done and multiplicity adjustment is not needed.

3. OBJECTIVES

3.1 Primary Objective

The primary objective is to evaluate the long-term safety and tolerability of SHP465 at 6.25mg administered as a daily morning dose in children aged 4-12 years (inclusive at the time of consent) diagnosed with Attention-deficit/Hyperactivity Disorder (ADHD).

The evaluation of safety and tolerability will be based on the occurrence of treatment-emergent adverse events (TEAEs), evaluation of vital signs (systolic and diastolic blood pressure and pulse), weight, height, body mass index (BMI); clinical laboratory and electrocardiogram (ECG) results; sleep assessment (Post Sleep Questionnaire [PSQ], and Children's Sleep Habits Questionnaire [CSHQ]); and responses to the Columbia-Suicide Severity Rating Scale (C-SSRS).

3.2 Secondary Objectives

The secondary objectives are:

- To describe the long-term efficacy of SHP465 using the clinician administered ADHD Rating Scale 5 (ADHD-RS-5) Child, Home Version.
- To describe the long-term efficacy of SHP465 using the Clinical Global Impressions–Improvement (CGI-I) scale.

4. SUBJECT POPULATION SETS

The following subject sets are applicable to this study:

4.1 Screened Set

The Screened Set will consist of all subjects who have provided informed consent.

4.2 Enrolled Set

The Enrolled Set will consist of all subjects who been assigned a subject identification number and enrolled at the Baseline Visit (Visit 2).

4.3 Safety Set

The Safety Set will consist of all subjects who have taken at least 1 dose of investigational product.

4.4 Full Analysis Set

The Full Analysis Set (FAS) will consist of all subjects in the Safety Set who have completed at least 1 post-dose efficacy assessment using ADHD-RS-5 Total Score.

5. SUBJECT DISPOSITION

A listing of all screen failures (ie, subjects who were screened but not enrolled) will be presented along with reasons for the failing the screening assessments and details of any reported adverse events (AEs).

All disposition data will be summarized for the Safety Set by treatment group in the antecedent studies (SHP465 or Placebo), current treatment (SHP465) for each enrollment type (rolled-over or directly enrolled), and current treatment (SHP465) for overall.

The number of subjects included in each analysis set (ie, Screened, Enrolled, Safety, and Full Analysis) will be summarized.

The number and percentage of subjects who completed and discontinued during the treatment period will be presented. The reasons for discontinuation from the treatment period, as recorded on the Study Completion page of the electronic case report form (eCRF), will be summarized (number and percentage). A subject who completes the final assessments and procedures specified at the final scheduled visit at the end of the treatment period (i.e., Visit 16) will have completed the study.

In addition, the number and percentage of subjects who completed the study visits will be presented.

Any subject who discontinued during the treatment period will be listed by discontinuation reason for the Safety Set.

Follow-up information, new (post-treatment) AEs and new (post-treatment) medication, will be listed for the Safety Set.

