## 8 ADVERSE AND SERIOUS ADVERSE EVENTS ASSESSMENT

### 8.1 Definition of Adverse Events, Period of Observation, Recording of Adverse Events

An AE is any untoward medical occurrence in a clinical investigation subject administered a pharmaceutical product and that does not necessarily have a causal relationship with this treatment. An AE can therefore be any unfavorable and unintended sign (including an abnormal laboratory finding), symptom, or disease temporally associated with the use of a medicinal (investigational) product, whether or not related to the medicinal (investigational) product (ICH Guidance E2A 1995).

All AEs are collected from the time the informed consent is signed until the defined follow-up period stated in Section 7.1.3. This includes events occurring during the screening phase of the study, regardless of whether or not investigational product is administered. Where possible, a diagnosis rather than a list of symptoms should be recorded. If a diagnosis has not been made, then each symptom should be listed individually. All AEs should be captured in the source documents. In addition to untoward AEs, unexpected benefits outside the investigational product indication should also be captured.

All AEs must be followed to closure (the subject's health has returned to his/her baseline status or all variables have returned to normal), regardless of whether the subject is still participating in the study. Closure indicates that an outcome is reached, stabilization achieved (the investigator does not expect any further improvement or worsening of the event), or the event is otherwise explained. When appropriate, medical tests and examinations are performed so that resolution of event(s) can be documented.

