8. EXTENT OF EXPOSURE AND TREATMENT COMPLIANCE

8.1 Exposure to Investigational Product

Exposure to the investigational product (SHP465) will be summarized for the Safety Set by treatment group of the antecedent studies, current treatment (SHP465) for each enrollment type, and overall. The following statistics will be calculated by visit for the investigational product:

- Days of dosing: number of days on which dose information was available and non-zero
- Total dose (mg) for SHP465: total number of capsules taken \times dose level
- Average daily dose (mg/day) for SHP465: the total dose / total days of dosing
- Cumulative dose (mg) for SHP465: sum of total dose since start of treatment

The following statistics will be calculated for the investigational product for the whole treatment period:

- Total days of dosing = sum of the number of days dosed for each visit during that period
- Duration of exposure in weeks = the total number of days dosed / 7 days per week
- Total dose (mg) for SHP465 = total number of capsules taken \times dose level
- Average daily dose (mg/day) for SHP465 = the total dose / total number of days of dosed

An appropriate statistical summary will be applied to each of the above statistical quantities.

Subjects will be categorized in 4 week increments by overall duration of exposure in days and will be presented by subject counts and percentages.

In addition, person-time (overall total exposure in days) will be derived for SHP465. It is calculated as the total number of days in which SHP465 was taken for each subject (total days of dosing for the Treatment period), and then sum over all subjects for the Treatment period.

All dosing information, for example, total dose, average daily dose and cumulative dose, will be listed.

If a bottle has missing start and end dates then the subject's dose information from this bottle will be treated as missing. In particular, for the subjects who are lost in the follow up after the Baseline Visit (Visit 2), it will not be assumed that any of the investigational product has been ingested unless there is a post-baseline safety assessment. The days, from which there are no records showing that subjects have taken investigational product, will be excluded from the calculation of exposure. Subjects that do not return the investigational product but return to the site for the following visit will have the dose return information entered into the database on the scheduled visit.

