11.1 Adverse Events

Adverse events will be coded using Version 18.0 of Medical Dictionary for Regulatory Activities (MedDRA).

An AE (classified by preferred term) that occurs during the treatment period will be considered a TEAE if it has a start date on or after the first dose of investigational product or if it has a start date before the date of the first dose of investigational product, but increases in severity on or after the date of the first dose of investigational product, and no later than 3 days following the last dose of investigational product. If more than 1 AE with the same preferred term is reported before the date of the first dose of investigational product, then the AE with the greatest severity will be used as the benchmark for comparison to the AEs occurring during the treatment period under the preferred term.

An overall summary of the number of subjects with TEAEs will be presented, including the number and percentage of subjects with any TEAEs, serious TEAEs, TEAEs related to investigational product, TEAEs leading to drug withdrawal, TEAEs by maximum severity, and serious TEAEs Leading to death.

The number and percentage of subjects reporting TEAEs will be tabulated by system organ class (SOC) and preferred term; by SOC, preferred term, and severity; and by SOC, preferred term, and relationship to investigational product. If more than 1 AE occurs with the same preferred term for the same subject, then the subject will be counted only once for that preferred term using the most severe and most related occurrence for the summarization by severity and by relationship to investigational product.

The incidence of common ($\geq 2\%$ of subjects in any treatment group of the antecedent studies, rollover or direct enroll group, or overall population) will be summarized by preferred term, sorted in decreasing frequency in the overall population. The incidence of TEAEs, serious TEAEs, and TEAEs leading to withdrawal will be summarized by SOC and preferred term, sorted in decreasing frequency in the overall population.

For the Safety Set, listings will be presented for all AEs, TEAEs related to investigational product, TEAEs leading to drug withdrawal, and serious TEAEs.

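### Disposition and AE listings run on the Safety Set leave out the withdrawal reason and any AE of a child enrolled at Visit 2 without a confirmed dose

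*SAP*

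**What the plan says.** SAP section 5 sets the population for completion, discontinuation and reasons: "All disposition data will be summarized for the Safety Set by treatment group in the antecedent studies". The subject-level listing follows suit: "Any subject who discontinued during the treatment period will be listed by discontinuation reason for the Safety Set". The same section also tabulates how many subjects fall in each of the Screened, Enrolled, Safety and Full Analysis Sets.

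For adverse events, SAP 11.1 says: "For the Safety Set, listings will be presented for all AEs".

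Membership is defined in SAP 4.3: "The Safety Set will consist of all subjects who have taken at least 1 dose of investigational product". The Enrolled Set (SAP 4.2) asks only for a subject number and enrolment at Visit 2. Both baseline-visit sections of the protocol (7.1.1.3 and 7.1.1.4) have drug dispensed at Visit 2 and dosing started the following morning.

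SAP 8.1, on exposure, adds a rule for subjects lost after Visit 2: "it will not be assumed that any of the investigational product has been ingested unless there is a post-baseline safety assessment".

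One other listing reports why a child did not go on and what AEs occurred, but for a different group: "A listing of all screen failures (ie, subjects who were screened but not enrolled) will be presented". On collection, Protocol 8.1 takes AEs from consent and adds: "This includes events occurring during the screening phase of the study, regardless of whether or not investigational product is administered".

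**The concern.** Between enrolment and the first confirmed dose there is a window in which a child belongs to the Enrolled Set but not to the Safety Set. Every output that would explain such a child's departure, or show an AE recorded for that child, is restricted to the Safety Set or to children never enrolled. A screen failure is therefore reported in more detail than a child who passed screening and was sent home with study drug. The documents give no reason for that ordering.

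Two things are at stake. First, discontinuation is part of how a long-term safety and tolerability study is read, and a denominator that omits some early losses gives a lower rate. Secondly, the protocol requires AEs and SAEs to be collected from consent whether or not drug is given. In Group B, screening and washout can last up to 32 days before Visit 2, so pre-dose events are possible. For these children such events would be collected but not listed.

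**Working it through.** The plan states no figure on this point, so there is nothing to reproduce. The check traces set membership and then gives an illustrative calculation.

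**Set membership**

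| Child | Enrolled Set | Safety Set | Reason and AEs listed? |
|---|---|---|---|
| (a) Enrolled, drug dispensed, no confirmed dose, no post-baseline safety assessment | Yes | No, if the SAP 8.1 rule is applied to membership | No |
| (b) Enrolled, known never to have taken a dose | Yes | No, by SAP 4.3 alone | No |
| (c) Enrolled, does not return, but a dose is known to have been taken | Yes | Yes | Yes |
| (d) Enrolled, dosing not recorded, but a post-baseline safety assessment exists | Yes | Yes, if SAP 8.1 is applied, since its exception is met | Yes |
| (e) Screened, not enrolled | No | No | Yes, in the screen-failure listing |

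The gap is rows (a) and (b). Row (a) rests on reading an exposure rule as a membership rule; row (b) does not.

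**Effect on the discontinuation rate**

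Let N be the number enrolled, D the number who discontinue, and k the number in rows (a) and (b). All k are discontinuations.

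- Enrolled Set rate: D/N
- Safety Set rate: (D − k)/(N − k)
- Difference: D/N − (D − k)/(N − k) = k(N − D)/[N(N − k)]

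The difference is positive whenever k ≥ 1 and at least one child completes, so the direction is fixed.

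For size, the inputs are:

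- N = 80 (SAP 2.5) or N = 145 (Protocol 9.6). The two documents differ on planned enrolment and should be reconciled; both values are carried here.
- 60 subjects completing 6 months, the target in both documents.
- D = N − 60, a simplification that treats everyone short of 6 months as discontinued. SAP 5 itself defines completion at Visit 16.
- k = 1 or 5, assumed; the documents give no value.

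| N | D | Enrolled Set rate | Safety Set rate, k = 1 | Safety Set rate, k = 5 |
|---|---|---|---|---|
| 80 | 20 | 20/80 = 25.0% | 19/79 = 24.1% | 15/75 = 20.0% |
| 145 | 85 | 85/145 = 58.6% | 84/144 = 58.3% | 80/140 = 57.1% |

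At N = 80 the differences are 0.9 and 5.0 percentage points; at N = 145 they are 0.3 and 1.5. In each case Enrolled minus Safety in the set-count table equals k.

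**The case against.** The strongest reply is that the gap is narrow and its main consequence is already visible. Several parts of that reply stand.

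- **The count is reported.** A reader might infer that these losses are concealed. They are not: the set counts in SAP 5 show how many there are. Reason, timing and AEs are what is missing.
- **Not every listing excludes them.** A reader might infer that such a child appears in no listing at all. The dosing (8.1), compliance (8.2), individual ECG (11.4) and C-SSRS (11.5.1) listings name no analysis set, and the listing specifications are in a separate document. None of these is described as carrying withdrawal reasons or AEs, so the narrower statement holds.
- **Membership is inferred in part.** SAP 4.3 does not refer to the 8.1 rule, and a known dose keeps a child in the Safety Set whatever 8.1 presumes.
- **A link to intolerance is not shown.** A reader might infer that the omitted children left because of side effects. Protocol 4.3.3 requires at least three documented contact attempts, and 4.3 and 7.2 ask for early-termination evaluations and the follow-up call. A parent who reports a dose and a reaction brings the child into the Safety Set. Those left out are mostly children with no informative contact after Visit 2, and changing the set cannot recover data never obtained. Moreover, rollovers from SHP465-112 and from the active arm of SHP465-309 had already received the 6.25 mg dose.
- **SAEs still reach the sponsor.** They are reported within 24 hours under Protocol 8.2.4, whatever the analysis set. The omission concerns the study report.
- **The study is descriptive and was stopped early.** No test is affected, and TEAE incidence is unchanged.

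This limits the consequence. It does not explain why a collected reason or AE should go unlisted for an enrolled child when a screen failure's is listed.

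**Conclusion.** The point holds as a bounded reporting gap. For an enrolled child with no confirmed dose and no post-baseline safety assessment, or one known never to have been dosed, the withdrawal reason and any AE or SAE since consent are in no discontinuation or AE listing that the SAP specifies. For the first kind of child, this depends on the SAP 8.1 rule being used to decide membership.

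The Safety Set discontinuation rate is below the Enrolled Set rate whenever such children exist and anyone completes. The size cannot be determined: k is not in the documents and may be zero. One such child moves the illustrative rate by under 1 percentage point at either planned N. The 5-point difference needs five such children among 80. No relative increase in loss to follow-up can be supported, since neither the number lost nor k is given.

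**What to change.** Three edits to the SAP:

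1. **Section 5.** Run the summary of completion, discontinuation and reasons, and the listing of discontinued subjects, on the Enrolled Set as SAP 4.2 defines it. Add a row for *dispensed, dosing not confirmed*. The SAP definition is the one to use: Protocol 9.7 rests on the subject number alone, which Protocol 6.2.2 assigns at consent, so it could take in screen failures.
2. **Section 11.1.** List AEs and SAEs for all enrolled subjects and flag those outside the Safety Set. Leave TEAE incidence on the Safety Set.
3. **Section 4.3.** State whether the no-ingestion rule in 8.1 decides Safety Set membership.

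The cost is small. The protocol already requires these data to be collected, and Protocol 9.4 leaves the disposition method to the SAP. Completion percentages may look slightly less favourable.
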